#### **7.4 SECONDARY ENDPOINT(S)**

All analysis will be descriptive and will be performed on FAS. For general condition of patients and patient's satisfaction with Spiolto® Respimat® as well as the willingness to continue the treatment, the number and percentage of patients within each category will be displayed. For absolute changes in CCQ scores (symptom, functional state (CCQ-4), mental state and total scale) summary statistics will be provided.

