## **9.7 DATA ANALYSIS**

### Planned analyses

More details will be described in the statistical analysis plan (SAP).

No formal hypothesis testing will be performed since this is a self-controlled study.

All patients who have received at least one dose of Spiolto® Respimat® will be included in the analysis; this is the treated set. All analyses will be performed on the treated set (as-treated analysis). If patients have missing values for an outcome, those patients will be excluded for that outcome's analysis. For example, if a patient is missing the CCQ score at

Visit 1 and/ or Visit 2, that patient will be excluded from the analyses for the primary endpoint of therapeutic success and the secondary endpoint of change in CCQs from Visit 1 to Visit 2.

The assessment will be carried out using SAS® software. The statistical characteristics presented in the end-of-text tables will be N / mean / SD / min / median / max for continuous variables. Tabulations of relative and absolute frequencies will be presented for categorical variables. Proportion rates and 95% CI will be given when appropriate.

The analyses will relate to the following data:

- Patient demographics (gender, age, height, weight)
- Comorbidities (main diagnosis and concurrent diagnosis according to MedDRA, version valid as at the time of database closure)
- COPD related and other concomitant medication (according to the WHO classification, version valid at the time of database closure)
- History of smoking
- Reported exacerbations
- Breathlessness based on mMRC score at visit 1
- Therapeutic success based on CCQ score; primary outcome
- Changes from Visit1 to Visit 2 in the CCQ and CCQ symptom, mental state and functional state scores; secondary outcome
- Patient reported daily average number of puffs of COPD rescue medication (eg. SABA, like Salbutamol) at the week before Visit 1 and the week before Visit 2
- Patient satisfaction with Spiolto® Respimat® at visit 2 only; secondary outcome
- General condition of the patient: evaluated by the physician (Physician's Global Evaluation (PGE)), secondary outcome
- Willingness to continue; secondary outcome
- Adverse Drug Reactions (ADR & SADR), fatal AEs, pregnancies
- GOLD spirometric classifications (1, 2, 3, 4) and GOLD patient groups (B, C, D)
- Details of treatment with inhaled respiratory agents before the study
- Details of treatment with respiratory agents during the study
- Reasons for ending treatment during the observation period

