#### **4. CHANGES IN THE PLANNED ANALYSIS OF THE STUDY**

- In addition to the protocol, subgroup analyses will be performed for all secondary endpoints, i.e. for changes from baseline in CCQ scores (symptom, functional state (CCQ-4), mental state and total scale), patient's satisfaction and willingness to continue treatment as well as PGE
- New analyses set, which is not mentioned in the protocol (Details are displayed in TSAP Section 6.3):
  - Full analysis set (FAS)

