### **6.3 PATIENT SETS ANALYZED**

**Full analysis set (FAS):** All screened patients with informed consent, date of registration (date of creation of screening form in the eCRF), and at least one documented administration of Spiolto® Respimat® and available total CCQ score at visit 1 and visit 2.

**Treated set (TS):** All screened patients with informed consent, date of registration (date of creation of screening form in the eCRF), and at least one documented administration of Spiolto® Respimat®.

Table 6.3: 1 Patient sets analyzed

Class of endpoint	Patient set	
	TS	FAS
Primary and secondary endpoints		X
Safety endpoints	X	
Demographic/baseline	X	

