### **7.3 PRIMARY ENDPOINT**

For the primary endpoint, the percentage of patients with therapeutic success will be presented together with the 95% confidence interval, whereupon therapeutic success is defined as 0.4-point decrease in CCQ score from visit 1 to visit 2. The number and percentage of patients with and without therapeutic success will be calculated for the whole FAS set and the above mentioned subgroups.

For comparison of subgroups,  $\chi^2$ -Test or Fisher's Exact test, if  $\chi^2$ -Test is not valid, will be used and p-values will be interpreted nominally. Additionally, 95% confidence intervals for the percentage of patients with therapy success will be calculated for each subgroup analyzed.

The total CCQ score ranges from 0 to 6. A higher score is indicative of worse status. If a patient fills in two answers on one question the data will be considered as missing. Missing values will not be imputed, one answer in the subscales “symptom” and “CCQ-4” might be missing, respectively, in order to calculate the total score. The total CCQ score and the corresponding subscales are calculated as followed, in case that at least the number of required answers is available:

Scale	Items	Items required	Scoring (For details see www.ccq.nl )
Symptom	1; 2; 5; 6	3	$\frac{\text{Sum of answered questions}}{\text{Number of answered questions}}$
Functional state (CCQ-4)	7-10	3	$\frac{\text{Sum of answered questions}}{\text{Number of answered questions}}$
Mental state	3; 4	2	$\frac{\text{Item 3 + 4}}{2}$
Total CCQ score	All subscales must be calculable		$\frac{(\text{Symptom} + \text{Functional state}) * 4 + (\text{Mental state}) * 2}{10}$

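### SAP 7.4 makes PGE, satisfaction and willingness to continue depend on a total CCQ at both visits, against protocol 9.7 and with no reason given in the visible text

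*SAP*

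**What the plan says.** Protocol 9.7 (Planned analyses) sets one rule for every analysis: "All analyses will be performed on the treated set (as-treated analysis"). Missing data are then handled outcome by outcome: "If patients have missing values for an outcome, those patients will be excluded" from that outcome only. The protocol's example says that a missing CCQ removes the patient from therapeutic success and from change in CCQ. It names nothing else.

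The SAP changes this. Section 4 lists the FAS as a "New analyses set, which is not mentioned in the protocol". Section 6.3 defines it as the treated set with one further condition: "and available total CCQ score at visit 1 and visit 2". In Table 6.3: 1 the row "Primary and secondary endpoints" is marked under FAS only. Section 7.4 repeats it, "All analysis will be descriptive and will be performed on FAS", and names general condition, satisfaction and willingness to continue among the outcomes covered.

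SAP 7.3 decides when a total CCQ exists. For the total score, "All subscales must be calculable". The symptom and functional scales each tolerate one missing item out of four; the mental-state scale tolerates none out of two. A double answer counts as a gap: "If a patient fills in two answers on one question the data will be considered as missing".

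**The concern.** Three secondary outcomes need no CCQ score: PGE at each visit, satisfaction at visit 2, and willingness to continue at visit 2. Under the SAP, a treated patient with these recorded is dropped from all three tables if the total CCQ is missing or cannot be scored at either visit. Two routes lead there:

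- **Missing visit 2 CCQ.** The patient's visit 1 PGE is lost, although the protocol asks for PGE at each visit and not for a paired change.
- **One unusable mental-state item.** A blank or double-marked item 3 or 4 at one visit removes a patient who attended both visits and answered everything else.

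The same gap also removes symptom and functional domain changes that could be calculated. That part is less clearly against the protocol, because its example of change in CCQ can be read to cover the domains.

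Willingness to continue is the protocol's proxy for adherence. The visit 2 schedule in Table 9.2.3.1 collects reasons for stopping treatment, so the study expects some attendees who have stopped. Selecting on completion of a different questionnaire is avoidable. If those excluded are less willing, the reported figure is too high. The missing-data category planned in SAP 7 cannot show them, because they are outside the set being tabulated.

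**Working it through.** **1. The two rules side by side**

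| Outcome | Protocol 9.7 requires | SAP 6.3 and 7.4 require |
|---|---|---|
| Therapeutic success, total-CCQ change | total CCQ at both visits | the same |
| PGE, visit 1 | PGE at visit 1 | also total CCQ at both visits |
| PGE, visit 2 | PGE at visit 2 | also total CCQ at both visits |
| Satisfaction | the answer | also total CCQ at both visits |
| Willingness to continue | the answer | also total CCQ at both visits |

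Only the first row is unchanged.

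**2. The plan's own figures (protocol 9.5)**

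With 50% success and n = 4050, 0.50 ± 1.96 × √(0.25/4050) = 0.50 ± 0.0154. This gives 48.5% to 51.5%, as stated. 4050/(1 − 0.10) = 4500, also as stated. On these figures up to 4500 − 4050 = 450 patients fall outside the FAS.

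**3. Possible shift in willingness**

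Let m be the number of patients outside the FAS with a recorded willingness answer, and w the proportion of them who are willing. Neither is given in the documents. Assume 95% willing in a FAS of 4050.

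Shift = 0.95 − (0.95 × 4050 + w × m)/(4050 + m) = (0.95 − w) × m/(4050 + m)

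| w (assumed) | m = 45 | m = 225 | m = 450 |
|---|---|---|---|
| 95% | 0 | 0 | 0 |
| 80% | 0.16 | 0.79 | 1.50 |
| 50% | 0.49 | 2.37 | 4.50 |
| 0% | 1.04 | 5.00 | 9.50 |

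Entries are percentage points by which the FAS exceeds the treated-set figure. The last row and last column are extremes.

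The 95% CI half-width is 1.96 × √(0.95 × 0.05/4050) = 0.67 points. The shift equals it at m = 0.0067 × 4050/(0.95 − w − 0.0067). That is about 190 for w = 80%, 61 for w = 50% and 29 for w = 0.

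**4. Loss among patients who attend both visits**

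Here 4050 is taken as the number of attendees, a different base from step 3. Assume each CCQ item is unusable independently with probability q; the documents give no rate.

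- Symptom or functional scale calculable at one visit: d = (1 − q)⁴ + 4q(1 − q)³
- Total scorable at both visits: [d² × (1 − q)²]²
- Symptom domain calculable at both visits: d²

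For q = 1%, d = 0.99941 and the total is scorable at both visits in 95.83%. So 4.17% are lost, about 169 of 4050. The symptom change is calculable in 99.88%, so 99.88% − 95.83% = 4.05%, about 164 patients, lose a usable symptom change. For q = 0.5%, 2.04% are lost, about 83 of 4050.

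This step measures lost data. It says nothing about bias unless those patients also answer differently.

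**The case against.** The strongest case on the other side has five parts.

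- **The set is declared.** SAP 4 lists the FAS as a departure from the protocol, and protocol 9.7 leaves detail to the SAP. The public SAP also has gaps in its numbering (5.3, 6.4 and 7.5 are absent), so a reason could stand in removed text. This limits the claim to the visible text. It does not remove the conflict, because SAP 4 as shown does not say that non-CCQ outcomes leave the treated set.
- **The selection is not demonstrated.** The CCQ is due at the same visit as satisfaction and willingness. A patient who has stopped treatment but completes both CCQs stays in the FAS, and one who misses visit 2 will usually have no satisfaction answer to lose. This stands. It makes m near 450 implausible for the visit 2 outcomes, but it does not cover visit 1 PGE or attendees with an unscorable CCQ.
- **The plausible shift is small.** If the 169 attendees from step 4 were 80% willing, the shift would be 0.15 × 169/4050 = 0.63 points, inside the 0.67-point half-width. The eCRF checks on missing entries may lower the item loss further. Both points are fair. At 50% willing the same 169 would give 0.45 × 169/4050 = 1.88 points, so a small effect is possible but not assured.
- **A common population has merit.** With available data at each visit, the two PGE tables hold different patients, and attrition mixes with change. This is a real cost, and FAS tables as a supplement meet it. The SAP already uses the treated set for baseline and safety, so it has no single denominator now.
- **Everything here is descriptive.** No formal hypothesis test is planned in the protocol, and the primary endpoint is untouched. That limits the severity.

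**Conclusion.** The concern holds. For PGE, satisfaction and willingness to continue, SAP 6.3 and 7.4 contradict protocol 9.7, and following the SAP discards recorded answers. The visible text gives no reason. Therapeutic success and total-CCQ change are the same under either rule. The point on domain changes is weaker, because the protocol's example can be read either way.

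The conflict rests on the wording alone. Its size rests on assumptions: the number excluded with an answer, how they answered, a 95% willingness rate in the FAS, and independent item loss. Across the assumed range the overstatement of willingness runs from zero to an extreme of 9.5 points. It passes the CI half-width at about 190 excluded answers if 80% of those patients are willing, or about 61 if 50% are. The direction is not established. This should be fixed, but it is confined to descriptive secondary tables.

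**What to change.** In SAP Table 6.3: 1 and Section 7.4, analyse PGE at each visit, satisfaction and willingness to continue in treated-set patients who have that outcome. Treat each CCQ domain change the same way; for the domains this also settles a point that the protocol leaves open. Show every denominator and the number missing, using the missing-data category already planned in SAP 7. Keep the FAS for the primary endpoint and total-CCQ change, and give FAS results for the other outcomes as a supplement, so that PGE at the two visits can also be read in one common group.

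If the FAS is to remain the main set, state the reason in SAP 4, say which outcomes leave the treated set, and add the treated-set tables as the supplement.

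The cost is SAP wording and a few extra tables from data already collected. Denominators will differ between secondary tables and must be shown, the main PGE tables may hold different patients at each visit, and satisfaction and willingness may look slightly less favourable.

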## **7.6 EXTENT OF EXPOSURE**

Not applicable.

## **7.7 SAFETY ANALYSIS**

The analysis of adverse events will be descriptive and conducted according to Boehringer Ingelheim standards. The main focus will be on treatment emergent events. All AE that occurred after signing the informed consent until the end of study (visit 2) will be considered as treatment emergent and will be displayed in frequency tables. Non treatment-emergent events will be assigned to “screening” or “post-treatment” and only be displayed in listings. All analyses will be based on the treated set.

In context of the presented study, only drug-related adverse events or events with fatal outcome (i.e., serious adverse events) will be documented. Their frequency and severity will be tabulated according to MedDRA-SOC and PT. Additionally adverse events (drug-related or serious ones) leading to treatment discontinuation will be presented. Moreover, the causality of events with fatal outcome will be displayed.

Unless otherwise specified, the analyses of drug-related adverse events and events with fatal outcome will be descriptive in nature. All analyses will be based on the number of patients with AEs and not on the number of events.

An overall summary of drug-related adverse events and events with fatal outcome will be presented.

The frequency of patients with drug-related adverse events or events with fatal outcome will be summarised by primary system organ class and preferred term. Separate tables will be provided for patients with serious adverse events.

The system organ classes will be sorted alphabetically, preferred terms will be sorted by frequency (within system organ class).

For analysis multiple AE occurrence data on the CRF will be collapsed into an AE event provided that all of the following applies:

- All AE attributes are identical (PT, severity, action taken, therapy required, seriousness, reason for seriousness, relationship, outcome)
- The occurrences were time-overlapping or time-adjacent (time-adjacency of 2 occurrences is given if the second occurrence started on the same day or on the day after the end of the first occurrence). For classification into TEAE or Non-TEAE, the first documented start of event will be used.

For further details on summarization of AE data, please refer to [3] and [4].

## **9. ADDITIONAL SECTIONS**

Not applicable.

## 10. HISTORY TABLE

Table 10: 1 History table

Version	Date (DD-MMM- YY)	Author	Sections changed	Brief description of change
Draft v0.1	18-JUL-2018		None	This is the first Draft-Version of TSAP without any modification
Draft v0.2	31-AUG-2018		6.2	Violation of A1.2 does not lead to exclusion of any analysis set
			6.3	Definition of analysis sets changed, i.e. "diagnosis of COPD in whom treatment with two long acting bronchodilators is indicated" no longer necessary to be analyzed
			6.4	Definition of "maintenance naïve" added
Draft v0.3	03-DEC-2018		4, 6.2, 6.3	Comments added, that have to be discussed
Draft v0.4	17-JAN-2019		4., 6.4	Subgroups adapted
Draft v0.5	22-FEB-2019		4., 6.4	Definition of treatment naïve added
Final 1.0	27-FEB-2019		6.3	Date of registration specified
Final 2.0	19-JUL-2019		7.7	Corrected "NCI-CTC grade" to "severity"
